### Model

For ease of presentation we assume that no censoring occurs. The below model will accommodate censoring.

For a subject  $i$  in the BIOFLOW-V study, if  $Y_{X,i}^V$  is the time to event, let

$$Y_{X,i}^V \sim \text{exponential}(\lambda_X^V) \quad \text{and} \quad Y_{O,i}^V \sim \text{exponential}(\lambda_O^V)$$

be the distributions of the time (years) to event in the Xience and Orsiro groups, respectively. The values  $\lambda_X^V$  and  $\lambda_O^V$  are the hazards in the Xience and Orsiro groups.

*Evidence from BIOFLOW-IV study:* It is first discounted using the discount factor  $a^{IV}$ . The discounted data are then assumed to follow exponential distributions with hazard rates  $\lambda_X^{IV}$  and  $\lambda_O^{IV}$  in the Xience and Orsiro groups, respectively. For a subject  $i$  in the BIOFLOW-IV study, if  $Y_{X,i}^{IV}$  is the time to event, let

$$Y_{X,i}^{IV} \sim \text{exponential}(\lambda_X^{IV}) \quad \text{and} \quad Y_{O,i}^{IV} \sim \text{exponential}(\lambda_O^{IV})$$

A bias term is assumed to link the TLF hazard rates in BIOFLOW-V and BIOFLOW-IV in each treatment group

$$\bullet \quad \log(\lambda_X^V) = \log(\lambda_X^{IV}) + \delta_X^{IV} \quad \text{and} \quad \log(\lambda_O^V) = \log(\lambda_O^{IV}) + \delta_O^{IV}$$

*Evidence from BIOFLOW- II study:* It is first discounted using the discount factor  $a^{II}$ . The discounted data are then assumed to follow Exponential distributions with hazard rates  $\lambda_X^{II}$  and  $\lambda_O^{II}$  in the Xience and Orsiro groups, respectively,

$$Y_{X,i}^{II} \sim \text{exponential}(\lambda_X^{II}) \quad \text{and} \quad Y_{O,i}^{II} \sim \text{exponential}(\lambda_O^{II})$$

A bias term is assumed to link the TLF rates in BIOFLOW-II and BIOFLOW-V in each treatment group.

$$\log(\lambda_X^V) = \log(\lambda_X^II) + \delta_X^II \text{ and } \log(\lambda_O^V) = \log(\lambda_O^II) + \delta_O^II$$

### Prior distribution

The bias terms are assumed to follow a normal distribution with mean 0 and standard deviation  $\tau_1$  and  $\tau_2$ .

$$\delta_X^II \sim \text{Normal}(0, \tau_1) \text{ and } \delta_O^II \sim \text{Normal}(0, \tau_1)$$

$$\delta_X^{IV} \sim \text{Normal}(0, \tau_2) \text{ and } \delta_O^{IV} \sim \text{Normal}(0, \tau_2)$$

As with primary endpoint analysis, a value of 0.3 will be assumed for both  $\tau_1$  and  $\tau_2$ . Non-informative prior distributions are assumed for TLF rates in the BIOFLOW-V study

$$\lambda_X^V \sim \text{gamma}(0.1, 0.1) \text{ and } \lambda_O^V \sim \text{gamma}(0.1, 0.1)$$

The non-inferiority condition will be expressed in terms of 1-year TLF rates in the BIOFLOW-V study as with the primary hypothesis

$$P(H_A | \text{Data}) = P(\pi_X^V - \pi_O^V > -\delta | \text{Data}) > \pi^*$$

where the 12-month TLF rates will be calculated as

$$\pi_X^V = 1 - \exp(-\lambda_X^V) \text{ and } \pi_O^V = 1 - \exp(-\lambda_O^V)$$

- 4) A tipping point analysis will be carried out. Here, it is assumed that for all Xience patients with missing primary endpoint (12-month TLF) status, TLF did not occur. For Orsiro patients with missing data, it will be first assumed that the primary endpoint of TLF occurred for exactly one such patient; then the primary analyses will be re-run to assess if non-inferiority is met under this assumption. Then it will be assumed the primary endpoint occurred for exactly two Orsiro patients with missing data, and the primary non-inferiority analysis will be rerun. The process will continue sequentially in this manner until all Orsiro patients with missing data are considered to have met the primary endpoint of TLF. Of interest is the “tipping point”, or i.e., the number of imputed Orsiro TLFs where non-inferiority is not met in this analysis.

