8.9. Handling of Missing Data in the Analysis of Primary Endpoint

Every effort will be undertaken to limit premature discontinuations and ascertain completeness of data collection. The following analysis strategies will be adopted to handle missing data with results compared for consistency prior to carrying out the above analysis:

1. Only subjects who experienced the primary endpoint (TLF at 12 months) or who had appropriate follow-up (at least 330 days post baseline, given the 30-day visit window allowed around the 12-month visit) will be included in the analysis.
2. All subjects will be included in the analysis set including data for subjects missing primary endpoint status due to not experiencing the event and not reaching at least 330 days of follow-up. Data for these subjects will be included as 'NA'. A model will be used for the event probabilities:

$$Y[i, j, k] \sim dbern(p[i, j, center[k]])$$

with

$$\text{logit}(p[i, j, center[k]]) = \beta * X[k] + \text{logit}(p[i, j])$$

where $X[k]$ are predictors values for subject k . A noninformative prior will be assumed on the slope parameters β and similarly to the analysis of the primary endpoint, bias will be assumed between TLF rates in different studies.

The following variables will be included in the model as covariates:

- Age
 - Gender
 - Diabetes
 - Lesion length
 - Others (the complete set will be detailed in the full SAP)
3. Time to event analysis using a Bayesian Cox regression analysis. For each study, a separate hazard ratio comparing Xience to Orsiro stent will be included. Similar to the method proposed as a primary method, a bias will be assumed between the hazard ratio of BIOFLOW-II or BIOFLOW-IV and the hazard ratio of the BIOFLOW-V. Further details will be provided in the full SAP.

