⁴ Smith SC Jr, Dove JT, Jacobs AK *et al.* ACC/AHA guidelines of percutaneous coronary interventions (revision of the 1993 PTCA guidelines) –Executive summary. A report of the American College of Cardiology/American Heart Association Task Force on Practice Guidelines (committee to revise the 1993 guidelines for percutaneous transluminal coronary angioplasty). *J Am Coll Cardiol* 2001;37:2215–2239.

MYOCARDIAL INFARCTION – PROTOCOL DEFINITION⁵

I. PCI (PERCUTANEOUS CORONARY INTERVENTION)

la. Baseline Biomarkers of Myocardial Damage

Periprocedural < 48 hours post PCI

A. Baseline CKMB and Troponin < 1*URL
 
Appropriate cardiac enzyme data:
 
a1. Confirmed by :
 
 - CKMB > 3*URL or - in the absence of CKMB, Troponin > 3*URL or - in the absence of CKMB and Troponin: CEC decision upon clinical scenario

B. Baseline CKMB or Troponin > 1*URL
 
Appropriate cardiac enzyme data:
 
b1. Confirmed by :
 
 - A rise in CKMB $\geq 50\%$ above the previous level and > 3* URL or - In absence of CKMB, a rise in Troponin $\geq 50\%$ above the previous level and > 3*URL. - in the absence of CKMB and Troponin: CEC decision upon clinical scenario 
AND
 
b2. Evidence that cardiac biomarker values were decreasing (e.g., two samples at least 4 hours apart) prior to the suspected MI.

C. New pathologic q waves in 2 contiguous ECG leads

URL = upper range limit, defined as 99th percentile of normal reference range

lb. If Baseline Biomarkers of Myocardial Damage: CK and/or CKMB > 1*URL or acute MI in progress

Myocardial infarction, re-infarction (extension) < 48 hours post PCI

A. If CK (or CKMB) from index MI has not yet reached its maximum level:
 
 - Recurrent thoracic chest pain or ischemia equivalent > 20 minutes (or new ECG changes consistent with MI)

⁵ Adapted from Vranckx P, Cutlip DE, Mehran R, Kint PP, Silber S, Windecker S, Serruys PW. Myocardial infarction adjudication in contemporary all-comer stent trials: Balancing sensitivity and specificity. Addendum to the historical MI definitions used in stent studies. *EuroIntervention* 2010;5:871–874.

AND

- Appropriate cardiac enzyme data:
 - A rise in CK within 24 hours of the index event $> 2 \times \text{URL}$ (confirmed by either CKMB or Troponin $> 1 \times \text{URL}$) and $\geq 50\%$ above the previous level or

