### 1.3 Primary Endpoint

The primary endpoint of the study is Target Lesion Failure (TLF) rate at 12 months post-index procedure. TLF is defined as all cardiac death, protocol-defined target vessel Q-wave or non-Q-wave myocardial infarction (MI), or clinically driven target lesion revascularization (TLR).

The TLF rate will be derived from events adjudicated by the CEC to be a cardiac death, protocol-defined Q-wave or non-Q-wave target vessel myocardial infarction, or a clinically-driven target lesion revascularization according to the CEC manual of operations and definitions.

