Clinical Monitoring	
 
• 100% source verification
 
• Independent core labs for angiography, IVUS & OCT
 
• On-site monitoring
 
• Independent CEC adjudication
 
	
 
• 100% source verification
 
• Independent angiographic core lab
 
• On-site Monitoring
 
• Independent CEC adjudication
 
	
 
• 100% source verification
 
• Independent angiographic core lab
 
• On-site Monitoring
 
• Independent CEC adjudication
 

To ensure the validity of data from subjects across trials, the following measures will be taken:

- Evaluation of the 12-month TLF rate (a primary endpoint in the BIOFLOW-V and a secondary endpoint in the BIOFLOW-II and IV trials) will be performed in a uniform fashion, using a consistent set of definitions and similar follow-up schedule:
  - The measurement schedule of cardiac enzymes is similar in all trials: cardiac enzymes are collected once within 6-24 hours post index procedure. While all trials mandated collection of CK and CKMB, the BIOFLOW-II also mandated measurement of troponin. The BIOFLOW-IV and BIOFLOW-V trials allow measurement of troponin if CK and CKMB are not used. To address the differences in the collection of

- cardiac enzymes between the three trials, a uniform definition of peri-procedural MI that is based on CK and CKMB levels (with troponin levels used only in the absence of CK and CKMB) will be utilized.
- All trials have similar clinical follow-up schedule at 1 month (telephone contact/clinic visit), 6 months (telephone contact/clinic visit) and 12 months (telephone contact/clinic visit for BIOFLOW-II clinic visit for BIOFLOW-IV and BIOFLOW-V).
  - The BIOFLOW-II and BIOFLOW-IV trials used the same independent angiographic core laboratory. To ensure consistency, angiograms from the BIOFLOW-II, BIOFLOW-IV and BIOFLOW-V trials will be analyzed or validated by the same angiographic core laboratory.
  - All clinical endpoints (potential TLR, MI and death events) will be re-adjudicated by the same independent CEC as will be employed for the BIOFLOW-V data, using uniform definitions.
- Data quality will be confirmed in accordance with the monitoring plan of each trial.
  - Only subjects that meet all BIOFLOW-V clinical and angiographic eligibility criteria will be included. The criteria include the following:

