## 2.8 Handling of Missing Data in the Analysis of Primary Endpoint

Every effort will be undertaken to limit premature discontinuations and ascertain completeness of data collection. The following analysis strategies will be adopted to handle missing data with results compared for consistency prior to carrying out the above analysis:

- 1) Only subjects who experienced the primary endpoint (TLF at 12 months) or who had appropriate follow-up (at least 330 days post baseline, given the 30-day visit window allowed around the 12-month visit) will be included in the analysis.
- 2) All subjects will be included in the analysis set including data for subjects missing primary endpoint status due to not experiencing the event and not reaching at least 330 days of follow-up. Data for these subjects will be included as 'NA'. Bayesian method will be used for the imputation. A model will be used for the event probabilities:

$$Y[i, j, k] \sim \text{dbern}(p[i, j, k])$$

with

$$\text{logit}(p[i, j, k]) = \beta * X[k] + \text{logit}(p[i, j])$$

where  $X[k]$  are predictors values for subject  $k$ . A noninformative prior will be assumed on the slope parameters  $\beta$  and similarly to the analysis of the primary endpoint, bias will be assumed between TLF rates in different studies.

The following variables will be included in the model as covariates:

- Age (>75, <=75)
- Gender
- Diabetes
- Lesion length (>26 mm, <=26mm)
- RVD (>2.75mm, <=2.75mm)

- 3) Time to event analysis using a Bayesian time to event exponential regression analysis. The protocol specifies that time to event analysis using a Bayesian Cox regression analysis will be performed as a sensitivity analysis but subsequently we determined that an exponential regression is better for allowing incorporating a bias term between the log hazard rates in BIOFLOW-V and BIOFLOW II and BIOFLOW-IV. For each study, a separate hazard ratio comparing Xience to Orsiro stent will be included. Similar to the method proposed as a primary method, a bias will be assumed between the log hazard of BIOFLOW-II or BIOFLOW-IV and the log hazard of the BIOFLOW-V.

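### The exponential time-to-event check assumes a constant TLF hazard although peri-procedural MI is confined to the first 48 hours; a two-piece hazard with a stated 12-month cut-off would remove a small bias

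*SAP*

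**What the plan says.** Protocol 8.9 item 3 planned a "Time to event analysis using a Bayesian Cox regression analysis" as one of four ways of handling missing 12-month TLF status. SAP 2.8 item 3 substitutes a "Time to event analysis using a Bayesian time to event exponential regression analysis". It discloses the change and gives a reason: an exponential model makes it easier to place a bias term between the log hazards of the three studies.

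The Model subsection gives each arm of each study a single hazard. The exponentials are said to "be the distributions of the time (years) to event in the Xience and Orsiro groups, respectively", and on drop-outs the SAP says only "The below model will accommodate censoring". The Prior distribution subsection sets the bias SD at 0.3, converts each BIOFLOW-V hazard to a 12-month rate by 1 - exp(-lambda) (the formula follows the words "where the 12-month TLF rates will be calculated as"), and applies the same absolute 3.85-point criterion and 0.975 threshold as the primary analysis. Item 3 states no censoring date, no check of the constant-hazard assumption and no piecewise alternative.

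SAP 1.3 counts target-vessel MI as a TLF component. The MI definition in Protocol Appendix B has a separate class headed "Periprocedural < 48 hours post PCI". SAP 2.2 says that "cardiac enzymes are collected once within 6-24 hours post index procedure", so this class is found mostly on about day 1.

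**The concern.** A Cox model leaves the shape of the baseline hazard free; a single exponential fixes it as flat. TLF has at least two phases: a burst in the first 48 hours and a lower hazard afterwards. One lambda averages them. A subject censored after day 2 can no longer have a peri-procedural MI, yet is carried to month 12 at a hazard that includes that risk.

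Item 3 models partial follow-up directly, and section 2.8 wants the four strategies compared for consistency. If item 3 disagrees with the others, the reader should be able to put that down to missing data and not to the shape of the model.

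**Working it through.** **Inputs**
- True 12-month TLF F = 7.0% in both arms, margin 3.85 points (SAP 2.5). At the margin Orsiro is 7.0 + 3.85 = 10.85%.
- Loss c = 10% (SAP 2.5). 1,200/0.90 = 1,333.3 reproduces the stated 1,334. The documents give no figure for the exponential analysis itself.
- Lower loss: in BIOFLOW-II, 287 + 148 = 435 of 452 completed 12 months (Protocol 8.1), so 17/452 = 3.8%, taken as 4%.
- Early share f of TLF: not in the documents. Protocol 3.5 gives 12-month TLR 3.5% against Orsiro TLF 6.5% in BIOFLOW-II, and 3.3% against 5.1% in BIOFLOW-III. The part that is not TLR is 1 - 3.5/6.5 = 46% and 1 - 3.3/5.1 = 35%. It also contains cardiac death and later MI, so these are rough ceilings, apart from subjects with both an early MI and a TLR. I use 30-50% as an assumption.
- Also assumed: a 12-month cut, with later events and drop-out spread evenly over the year.

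**Formulas.** With e = fF and l = F - e:
- expected events d = e + l(1 - c/2)
- person-years PT = (1 - e)(1 - c/2) - l(1/2 - c/3)
- lambda = d/PT, rate = 1 - exp(-lambda)

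**Worked case** (f = 50%, c = 10%): e = l = 0.035. d = 0.035 + 0.035 × 0.95 = 0.06825. PT = 0.965 × 0.95 - 0.035 × 0.4667 = 0.9004. lambda = 0.0758, rate = 7.30%. The later hazard alone is 0.035 × 0.95/0.9004 = 0.0369 per year, so drop-outs are projected at about twice the hazard they face.

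| Loss | f | Rate when truth is 7.0% | Rate when truth is 10.85% | Difference (truth 3.85) |
|---|---|---|---|---|
| 0% | 30% | 7.07% | 11.02% | 3.95 |
| 0% | 50% | 7.12% | 11.14% | 4.02 |
| 4% | 30% | 7.11% | 11.08% | 3.97 |
| 4% | 50% | 7.19% | 11.25% | 4.05 |
| 10% | 30% | 7.18% | 11.17% | 4.00 |
| 10% | 50% | 7.30% | 11.41% | 4.11 |

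The rows with no loss show that 0.07-0.12 points come from misfit alone. Loss adds the rest.

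**Where the direction changes**
- Later events all in months 6-12, f = 25%, 10% loss spread evenly: 6.92%, an understatement. With the same events but all drop-out at day 30: 7.09%.
- Times not cut at 12 months (f = 50%, later hazard constant at 0.0369, no loss): two years give events 1 - 0.965 exp(-0.0739) = 0.1037 over 0.965(1 - exp(-0.0739))/0.0369 = 1.860 person-years, a rate of 5.4%. The same formula over five years gives 0.1978/4.406, a rate of 4.4%. These are single-study rates before discounts and bias terms.

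**Two-piece model, same inputs** (f = 50%, c = 10%): lambda1·t1 = -ln(1 - 0.035) = 0.0356. lambda2 = 0.0369. The rate is 1 - exp(-0.0726) = 7.00%.

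**The case against.** The strongest reply is that this is one sensitivity analysis among several. The primary analysis is binomial, a tipping-point analysis is planned, and SAP 2.13 plans the primary endpoint without peri-procedural MIs. The change from Cox is disclosed and reasoned. Historical subjects enter only with an event or at least 330 days of follow-up (SAP 2.6.4), so early drop-out projection concerns BIOFLOW-V alone. Protocol 5.3.2.1 bars exit as lost to follow-up before the 12-month visit, so 10% may be high, although withdrawals and missed visits can still censor. Item 3 is also not the worse method: under the same even-spread assumptions at 10% loss, the complete-case rule in item 1 gives about 7.4-7.5%, against 7.2-7.3% here. All of this stands and keeps the point small. It does not justify a constant hazard. The analysis without peri-procedural MIs is planned on the primary endpoint and does not repair item 3.

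A reader might infer four stronger things, none of which the documents support:
- *The rates are always overstated.* A definition gives a window, not a share, and the sign depends on later timing and on the cut-off. BIOFLOW-II had mandatory 9-month angiography, which could bring TLR late.
- *Drop-out is the whole cause.* The misfit is present with complete follow-up.
- *Different event timing between arms creates a false difference.* An early share of 70% in one arm and 30% in the other would produce 7.43 - 7.18 = 0.25 points at 10% loss, but nothing in the documents suggests such a contrast.
- *Five-year historical data will pull the rates far down.* Section 2.8 concerns a 12-month endpoint, and Protocol 8.10 censors its secondary time-to-event analyses at the end of the relevant period. BIOFLOW-IV, enrolled from September 2013, could not have five-year data by the April 2017 date in SAP section 3. What remains is an unstated cut-off, which one sentence settles.

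**Conclusion.** The point holds in a limited form. A single hazard does not suit an endpoint with a component confined to 48 hours. Given a 12-month cut, roughly even later events and an early share of 30-50%, item 3 overstates each arm's 12-month TLF by about 0.1-0.2 points at 4% loss and 0.2-0.3 points at 10% loss. At the margin the difference is read about 0.1-0.3 points too large, which makes non-inferiority harder to declare. With equal rates, timing and loss in the two arms the bias cancels.

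The early share, the even spread of later events and the 12-month cut are assumptions; the first is not in the documents and the last is not stated in item 3. No stated figure in the plan is wrong on this point, and the primary conclusion does not depend on it. This is a cheap improvement of low severity.

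**What to change.** In SAP 2.8 item 3:
- Use a piecewise exponential with a cut at t1 = 48 hours (2/365 year) or 30 days, and two hazards per arm and study.
- Keep the Normal(0, 0.3) bias terms on the log hazards and the same discounts. This preserves the stated reason for leaving Cox. Say whether one bias term per arm and study shifts both pieces or each piece has its own.
- Compute pi = 1 - exp(-(lambda1·t1 + lambda2·(1 - t1))).
- State that all three studies are censored at the 12-month cut-off used for primary TLF.

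One detail needs care with the 48-hour cut. 400 Xience subjects contribute only about 400 × 2/365 = 2.2 person-years to the first piece, so the rate parameter of the gamma(0.1, 0.1) prior is no longer negligible (0.1/2.2 = 5%, before borrowing). Putting the prior on lambda1·t1, or cutting at 30 days (400 × 30/365 = 33 person-years, 0.3%), avoids this.

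Cost: a few lines of OpenBUGS code and of SAP text, and one more hazard per arm and study, with negligible loss of precision.

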## 2.9 Analysis of Secondary Endpoints

The secondary endpoints in the BIOFLOW-V study will be analyzed using frequentist methods. For each endpoint, the proportion and sample size will be calculated and reported for the Xience group and for the Orsiro group. Fisher’s exact test will be used to test the difference between the groups. Analyses of secondary endpoints will be carried out on the ITT, Modified ITT and PP analysis sets for BIOFLOW-V. However, there will be no direct imputation of missing data. Secondary Endpoints include the following measures:

- 1) Device success
- 2) Lesion success
- 3) Procedure success

BIOFLOW-V will utilize the percent residual stenosis, as assessed by the investigator for the primary analysis measure of the % residual stenosis for evaluating angiographic success for the aforementioned secondary endpoints. If investigator assessment of residual stenosis is not available, the in stent final % diameter stenosis as assessed by QCA will be used. MACE included in the procedure success will use the primary analysis definitions.

Treatment group difference (Orsiro minus Xience) in the success rates and the two-sided 95% confidence intervals of the difference will be presented.

The following secondary clinical endpoints will be evaluated prior to discharge, at 1-, 6- and 12-months and annually:

- 4) Death
- 5) Protocol-defined MI
- 6) Cardiac death or protocol-defined MI
- 7) MACE and individual MACE components
- 8) TLF and individual TLF components
- 9) TVF and individual TVF components
- 10) Stent thrombosis according to ARC criteria

Included in the analysis, will be subjects experiencing the event or who have adequate follow-up (e.g., at least 23 days for 1-month time point, at least 166 days for the 6-month time point, and at least 330 days for the 12-month time point).

All the re-adjudicated clinical endpoints in BIOFLOW-II and BIOFLOW-IV will be summarized by study and treatment group.

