Prime™ ($0.16 \pm 0.33 \text{ mm}^2$ vs. $0.43 \pm 0.56 \text{ mm}^2$, respectively; $P = 0.0428$). The pre-specified secondary OCT endpoints at 9 months showed a significant difference in tissue coverage between the Orsiro and the Xience Prime™ groups (98.3 vs. 97.5%, respectively; odds ratio 1.51; 95% confidence interval [CI] 1.02, 2.45; $P = 0.042$). At 9 months, the Orsiro stent was associated with thinner neointima thickness (0.094 vs. 0.119 mm, $P < 0.001$). No significant differences in incomplete strut apposition (ISA) were found between the treatment groups at 9 months.

BIOFLOW-III

The BIOFLOW-III study is an open-label prospective, non-randomized, multicenter, international, observational all-comers registry that enrolled a total of 1,356 subjects at 43 centers in 14 countries across Europe and Chile (clinicaltrials.gov identifier NCT01553526). The purpose of the registry was to evaluate safety and performance of the Orsiro Sirolimus Eluting Stent (SES) in a large series of subjects under real-world conditions.

The primary endpoint was the 12-month rate of TLF, defined as cardiac death, target vessel Q-wave or non-Q-wave MI, emergent CABG or clinically driven TLR. The first subject was enrolled in August 2011 and enrollment was completed in March 2012. The subjects are currently in the follow-up phase of the trial.

The BIOFLOW-III registry enrolled an unselected subject population, including a high proportion of high-risk subjects presenting with diabetes (29.6%), small vessels (42.4%), acute MI (32.6%), and chronic total occlusions (4.3%). The rate of TLF was 5.1% at 12 months. The rate of ARC-defined definite or probable stent thrombosis at 12 months was 0.4%.

While BIOFLOW-I and II had mandatory angiographic follow-up and BIOFLOW-III did not, rates of 12-month TLR were 6.7%, 3.5%, and 3.3% for BIOFLOW-I, II and III, respectively.

Among subgroups, 12-month TLF rates were 7.7% in subjects with diabetes compared with 4.0% in non-diabetics, and 7.2% in subjects with acute myocardial infarction (AMI) compared with 4.0% in subjects without AMI.

BIOFLOW-IV

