Of the 2119 subjects (3139 lesions) included in the study, 407 (19%) patients presented with ST-segment elevation myocardial infarction. A total of 1063 subjects (1594 lesions) were randomized to receive the Orsiro stent and 1056 patients (1545 lesions), were randomized to receive the Xience stent. At 12 months, the TLF rate for the Orsiro stent (69 subjects, 6.5%) was non-inferior to the Xience stent (70, 6.6%) at 12 months (absolute risk difference -0.14% , upper limit of one-sided 95% CI 1.97% , p for non-inferiority <0.0004). No significant differences were noted in rates of clinical events, including stent thrombosis.

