### 1.1 Trial Objective

The objective of this study is to assess the safety and efficacy of the Orsiro Sirolimus Eluting Coronary Stent System in the treatment of subjects with up to three native *de novo* or restenotic (standard PTCA only) coronary artery lesions compared to the Xience coronary stent system.

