## 2 PLANNED ANALYSES

### 2.1 General Analysis Definitions

Bayesian analyses will be performed using the open-source program OpenBUGS version 3.2.3 (Bayesian inference using Gibbs Sampling), Lunn et al.; other analyses, including summaries, will be conducted using SAS (version 9.4), unless otherwise noted. Descriptive statistics for continuous variables will include mean, standard deviation, median, quartiles, minimum, maximum, and sample size for each treatment group. Categorical variables will be summarized using counts and percentages. Proportions will be calculated using known non-missing values. Unless otherwise indicated, all statistical tests and/or confidence intervals will be performed at  $\alpha = 0.05$  (2-sided).

---

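### SAP 2.9 gives all-cause death, any MI, MACE, TVF and stent thrombosis a Fisher test but no treatment difference with an interval, and drops the Bayesian estimates of protocol 8.10 without giving a reason.

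*SAP*

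**What the plan says.** SAP 1.1 sets the aim: "The objective of this study is to assess the safety and efficacy of the Orsiro Sirolimus Eluting Coronary Stent System". SAP 2.9 then analyses the secondary endpoints in BIOFLOW-V data by frequentist methods. For each endpoint "the proportion and sample size will be calculated and reported for the Xience group and for the Orsiro group", and a Fisher "exact test will be used to test the difference between the groups". The level is the general default of SAP 2.1, where "all statistical tests and/or confidence intervals will be performed at" a two-sided 0.05.

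After the device, lesion and procedure success endpoints, SAP 2.9 adds: "Treatment group difference (Orsiro minus Xience) in the success rates and the two-sided 95% confidence intervals of the difference will be presented". The clinical endpoints 4 to 10 (death, MI, cardiac death or MI, MACE, TLF, TVF, stent thrombosis) come after that sentence, and nothing comparable is written for them.

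SAP section 3 keeps a combined Bayesian analysis for TLF and its components and rules it out for the other secondary endpoints. Protocol 8.10 reads differently. It assigns all secondary endpoints to the method used for the primary endpoint, and adds Bayesian Cox regression with a hazard ratio per study for time-to-event endpoints. SAP 2.8 explains a move away from Cox regression, but only for the missing-data analysis of the primary endpoint.

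**The concern.** Protocol 13.2 names fewer late and very late stent thromboses as the possible benefit of the Orsiro stent, and safety is half of the stated objective. Yet the only comparative output planned for stent thrombosis, all-cause death and any MI is a p-value. With few events, a p-value above 0.05 is the expected result whether or not Orsiro is worse. It cannot separate a result that rules out a sizeable excess from one with too few events to tell. The SAP does plan an interval for the success rates, and SAP 2.11 plans a credible interval for the TLF difference in every subgroup. An exploratory subgroup thus gets an estimate with uncertainty, while stent thrombosis in the whole trial does not.

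**Working it through.** **Sample size.** The documents state no power for any secondary endpoint; the 89.6% in SAP 2.5 is for TLF non-inferiority. The figures to reproduce are the group sizes. 1,200 / 0.90 = 1,333.3, rounded up to 1,334; 1,260 / 0.90 = 1,400. Both match. The evaluable sizes are 800/400 (SAP 2.5) and 840/420 (protocol 8.5), and the maximum randomized is 933/467.

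**Stent thrombosis rate.** The plan assumes none. Protocol 3.5 reports for BIOFLOW-III: "The rate of ARC-defined definite or probable stent thrombosis at 12 months was 0.4"%. Using this single-arm Orsiro figure as the Xience rate is my assumption. At 840/420, a doubling means about 840 × 0.008 = 6.7 Orsiro events against 420 × 0.004 = 1.7 Xience events.

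**Power.** Sum, over all pairs of event counts (a, b), Bin(a; n_O, p_O) × Bin(b; n_X, p_X) wherever the two-sided Fisher p is at most 0.05. For 0.4% against 0.8%:

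- 800/400: power 4.6%, missed 95.4%
- 840/420: power 5.2%, missed 94.8% (5.0% if only rejections against Orsiro are counted)
- 933/467: power 6.6%, missed 93.4%

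**Sensitivity to the Xience rate, for a doubling:**

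| Xience rate | Power 800/400 | Missed 800/400 | Power 840/420 |
|---|---|---|---|
| 0.2% | 0.6% | 99% | 0.7% |
| 0.4% | 4.6% | 95% | 5.2% |
| 1% | 20% | 80% | 21% |
| 2% | 42% | 58% | 44% |
| 3% | 61% | 39% | 64% |
| 5% | 86% | 14% | 88% |
| 7% | 96% | 4% | 97% |

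The last row is the relevant one for MACE and TVF. By definition each includes essentially every TLF event, so under the plan's own 7.0% TLF assumption they should run at about 7% or more.

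**Threshold.** With 2 Xience events, 16 Orsiro events are needed for significance. At 840/420 that is 1.90% against 0.48%, a fourfold rate.

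**What an interval adds.** The Newcombe interval uses the Wilson limits (l, u) of each arm. Its lower limit is d − √[(p_O − l_O)² + (u_X − p_X)²]; its upper limit is d + √[(u_O − p_O)² + (p_X − l_X)²].

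For 10/840 against 2/420, in percentage points: p_O = 1.19 (Wilson 0.65 to 2.18), p_X = 0.48 (0.13 to 1.72), d = 0.71.

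- Lower: 0.71 − √(0.54² + 1.24²) = −0.64
- Upper: 0.71 + √(0.99² + 0.35²) = 1.76

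| Orsiro | Xience | Fisher p | Difference (points) | 95% interval |
|---|---|---|---|---|
| 10/840 | 2/420 | 0.36 | +0.71 | −0.6 to +1.8 |
| 7/840 | 2/420 | 0.73 | +0.36 | −1.0 to +1.3 |
| 3/840 | 2/420 | 1.0 | −0.12 | −1.4 to +0.7 |

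All three read as not significant, but the upper limits differ by a factor of about 2.7 (1.76 / 0.65).

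**Other sources of an interval.** Among the endpoints in question, SAP section 3 covers only cardiac death, target-vessel MI and target lesion revascularization, as TLF components. SAP 2.12 gives a posterior probability that Orsiro exceeds Xience for AEs and SAEs with a frequency above 10. It works on site-reported terms, not adjudicated endpoints, and plans no interval. Neither supplies one for all-cause death, any MI, MACE, TVF or stent thrombosis.

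**The case against.** A reader might infer that the plan will treat a non-significant Fisher test as proof of safety. The documents do not say so. The nearest text is the protocol 3.5 summary of BIOSCIENCE, "No significant differences were noted in rates of clinical events, including stent thrombosis", which is background on another trial and sets no rule for this one.

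A reader might also carry the 95% figure over to every clinical endpoint. That would be wrong: it belongs to stent thrombosis at an assumed 0.4%, from an all-comers registry with many acute MI patients, and the table shows good power at MACE and TVF rates.

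Nor does the whole safety assessment hang on Fisher tests. Cardiac death and target-vessel MI keep a Bayesian analysis, SAP 2.7.3 adds an ARC-MI sensitivity analysis, SAP 2.12 compares adverse events, and an unblinded DMC reviews safety.

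Finally, since SAP 2.9 reports proportions and sample sizes, any reader can derive an interval. An interval adds no power, and without a stated threshold it does not decide what excess is acceptable.

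These points limit the size of the concern. They do not fill the gap: an interval derived afterwards has neither a pre-specified method nor a pre-specified interpretation, and the departure from protocol 8.10 remains unexplained.

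**Conclusion.** The point holds as a gap in estimation and an unexplained change from the protocol. In the SAP, all-cause death, any MI, MACE, TVF and stent thrombosis have no planned effect estimate with uncertainty, although the success rates do and the protocol had planned model-based estimates. The practical loss is greatest for rare events. At an assumed 0.4% Xience rate the Fisher test misses a doubling of stent thrombosis about 95% of the time at 840/420. Over assumed rates of 0.2% to 1% the miss rate is about 99% to 80% at 800/400, so the conclusion for rare events does not depend on the exact rate. For MACE and TVF the complaint is only the missing interval, since power for a doubling from about 7% is about 97%. The primary TLF conclusion, the sample size and data collection are unaffected.

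**What to change.** In SAP 2.9, extend the sentence now limited to success rates. For endpoints 4 to 10 at each time point, present the Orsiro-minus-Xience difference with a two-sided 95% confidence interval by a small-count method such as Newcombe or Miettinen-Nurminen. State that statements on rare safety events will report the upper limit, and that a Fisher p above 0.05 will not be treated as evidence of no difference. Reconcile SAP 2.9 with protocol 8.10: either restore the Bayesian and time-to-event estimates for these endpoints, or record that they were dropped and why.

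The cost is one more column in existing tables and a short explanatory paragraph; no new data are needed. The downside is that wide intervals will show plainly that this trial does not settle rare-event safety.
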